10.5.4 Concomitant Medications

All concomitant medications will be collected and recorded on the source documents and eCRF from Screening through end of study.

11 Safety Reporting

The Sponsor maintains a robust pharmacovigilance system comprised of a governance framework and standard operating procedures supporting a systematic process for review, evaluation, and management of accumulating safety data from clinical trials and other sources to:

- Identify a potential new safety signal;
- Ensure that an investigational product's risks are adequately assessed and communicated to investigators, IRBs/IECs, and regulatory bodies during clinical development.

Findings and/or safety data obtained during this study will provide information for the overall review of safety that is conducted by the Sponsor on a routine basis. The Sponsor will report expeditiously any findings from clinical trials (ongoing or completed), epidemiological studies, pooled analysis of multiple studies, and findings from animal or in vitro testing that suggest a significant risk in humans exposed to the study product.

Safety data collection for this study begins at the time of the subject's signing of the informed consent document according to the operating definitions defined in this section of the protocol. The investigator is responsible for the detection and documentation of events that meet the definition of an unanticipated problem (refer to protocol Section 10.1), AE or SAE.

11.1 Operating Definitions for Assessing Safety

11.1.1 Adverse Event

An AE is any untoward medical occurrence in a patient or clinical investigation subject administered a study product and which does not necessarily have a causal relationship with the treatment.

An AE can therefore be any unfavorable and unintended sign (that could include a clinically significant abnormal laboratory finding), symptom, or disease temporally associated with the use of a study product, without any judgment about causality (i.e., whether or not considered related to the study product).

Additionally, an event that is associated with study participation (regardless of administration of or relationship to study drug) should be treated as a reportable adverse event for this protocol (e.g., complications resulting from the taking of a blood sample or performance of a protocol required procedure).

An AE **does** include the following:

• Exacerbation or worsening of a pre-existing illness.

NOTE: If the pre-existing illness is the disease under study, then "exacerbation" refers to an unexpected worsening from the condition at baseline.

- Increase in frequency or intensity of a pre-existing episodic event or condition.
- Condition detected or diagnosed after study product administration even though it may have been present prior to the start of the study.
- Symptom associated with disease not previously reported by the subject.

An AE **does not** include the following:

- Medical or surgical procedures (e.g., surgery, endoscopy, tooth extraction, transfusion) as event terms; the condition that led to the procedure is the AE if it meets the definition of an AE.
- Situations where an untoward medical occurrence has not occurred (e.g., hospitalization for cosmetic elective surgery; and social and/or convenience admissions).
- Overdose of either study product or concurrent medication without any signs or symptoms.
- Symptoms associated with disease, which are consistent with the subject's usual clinical course; unless the subject experiences worsening of their symptom(s) or the symptom(s) meet the criteria for an SAE.

11.1.2 Serious Adverse Event

A SAE is any AE, occurring at any dose, which results in any of the following outcomes ("Occurring at any dose" does not imply that the subject received study product.):

- Results in death.
- Is life threatening.

NOTE: Life-threatening means that the subject was, in the view of the investigator or Sponsor, at immediate risk of death at the time of the event. This definition does not refer to an event which hypothetically might have caused death if it were more severe.

- Requires inpatient hospitalization or prolongation of existing hospitalization.
- Clinical Study Protocol Amendment 1 08Oct2018

NOTE: Complications that occur during hospitalization are AEs. If a complication prolongs hospitalization or fulfills any other serious criteria, the event is serious. Hospitalization for elective treatment of a pre-existing condition that did not worsen from baseline is not considered to be an AE. "In-patient" hospitalization means the subject has been formally admitted to a hospital for medical reasons. This may or may not be overnight. It does not include presentation at a casualty or emergency room.

• A persistent or significant incapacity or substantial disruption of the ability to conduct normal life functions.

NOTE: The term disability means a substantial disruption of a person's ability to conduct normal life functions. This definition is not intended to include experiences of relatively minor medical significance such as uncomplicated headache, nausea, vomiting, diarrhea, influenza, or accidental trauma (e.g., sprained ankle) that may interfere or prevent everyday life functions but do not constitute a substantial disruption.

- A congenital anomaly or birth defect in the offspring of a subject who received study product.
- Important medical events that do not result in death, are not life-threatening, or require hospitalization may be considered an SAE when, based upon appropriate medical judgment, they may jeopardize the subject and may require medical or surgical intervention to prevent one of the outcomes listed in this definition.

NOTE: Examples of such medical events include allergic bronchospasm requiring intensive treatment in an emergency room or at home, blood dyscrasias or convulsions that do not result in inpatient hospitalization, or the development of drug dependency or drug abuse.

11.1.3 Assessment of Severity

The severity assigned to an AE should be determined by the maximum severity of the AE. The categories described below should be used to estimate the severity of AEs:

- Mild: Transient or mild discomfort; no limitation in activity; no medical intervention/therapy required
- Moderate: Mild to moderate limitation in activity; some assistance may be needed; no or minimal medical intervention/therapy required
- Severe: Marked limitation in activity; some assistance usually required; medical intervention/therapy required; hospitalization or prolongation of current hospitalization possible; may be incapacitating or life threatening

Clinical Study Protocol Amendment 1 08Oct2018

11.1.4 Assessment of Causality

The investigator should assess the relationship of the AE, if any, to the study drug using the following definitions:

Related: Event or laboratory test abnormality with reasonable time relationship to drug intake. Cannot be attributed to disease or other drugs. Response to withdrawal is clinically reasonable and re-challenge is not required.

Probable: Event or laboratory test abnormality with reasonable time relationship to drug intake. Unlikely to be attributed to disease or other drugs. Response to withdrawal is clinically reasonable and re-challenge is not required.

Possible: Event or laboratory test abnormality with reasonable time relationship to drug intake. Could also be explained by disease or other drugs. Information on drug withdrawal may be lacking or unclear.

Unlikely: Event or laboratory test abnormality with a time to drug intake that makes a relationship improbable (but not impossible). Disease or other drugs provide plausible explanations.

Not Related: Event or laboratory test abnormality with a time to drug intake that makes a relationship implausible. Disease or other drugs provide plausible explanations.

11.2 Clinical Laboratory Abnormalities and Other Abnormal Assessments as AEs and SAEs

Abnormal laboratory findings (e.g., clinical chemistry, hematology) or other abnormal assessments (e.g., abnormal findings during examinations or ECG monitoring) that are judged by the investigator as **clinically significant** must be recorded as AEs or SAEs if they meet the definition of an AE or SAE. The investigator should exercise his or her medical and scientific judgment in deciding whether an abnormal laboratory finding or other abnormal assessment (including ECG monitoring) is clinically significant.

11.3 Method and Frequency for Detecting AEs and SAEs

At each visit, after the subject has had an opportunity to spontaneously mention any problems, the investigator should inquire about AEs by asking the following standard questions:

1. "Have you had any (other) medical problems since your last visit/assessment?"

2. "Have you taken any new medicines, other than those given to you in this study, since your last visit/assessment?"

11.3.1 Time period for Detecting and Reporting of AEs and SAEs

From the time of informed consent through study completion/withdrawal, including the follow-up period.

11.3.2 Post-Study SAEs

Investigators are not obligated to actively seek SAE information in former study participants, but investigators are encouraged to notify the Sponsor of any SAEs of which they become aware occurring at any time after a subject has discontinued or completed the study that they judge may be reasonably related to study treatment or study participation.

11.4 Documenting AEs and SAEs

All AEs that occur after the subject has signed the informed consent document and during the course of the study, regardless of causality or seriousness, will be assessed and recorded in the subject's medical records and in the eCRF. In addition, SAEs must be documented on the paper SAE Report Form.

A separate paper SAE Report Form should be used for each SAE. However, if at the time of initial reporting, multiple SAEs are present that are temporally and/or clinically related, they may be reported on the same SAE Report Form.

The investigator should attempt to establish a diagnosis for the event based on signs, symptoms, and/or other clinical information. In such cases, the diagnosis should be documented as the AE and SAE and not the individual signs/symptoms.

For clinically significant abnormal laboratory findings or other abnormal assessments meeting the definition of an AE or SAE, a diagnosis, if known (or clinical signs and symptoms if diagnosis is unknown), should be recorded by the investigator. If a diagnosis is unknown and clinical signs and symptoms are not present, then the abnormal finding should be recorded. When documenting as an SAE on the SAE Report Form, relevant laboratory data should either be recorded in the 'Details of Relevant Assessments' section of the SAE Report Form (including the reference range and units) or copies of the laboratory report (with reference ranges and units) should be sent with the SAE Report Form.

The SAE Report Form should be completed as thoroughly as possible and signed by the investigator or his/her designee before transmittal to the CRO. It is **very important** that the

investigator provide his/her assessment of causality to study product at the time of initial SAE reporting.

11.5 Follow-Up of AEs and SAEs

All AEs, regardless of seriousness, must be followed until resolution, until the condition stabilizes, until the event is otherwise explained, or the subject is lost to follow-up. The investigator is responsible to ensure that follow-up includes any supplemental investigations as may be indicated to elucidate as completely as practical the nature and/or causality of the AE. This may include additional laboratory tests or investigations, histopathological examinations, relevant hospital records (i.e., discharge summary), or consultation with other health care professionals.

The Sponsor may request that the investigator perform or arrange for the conduct of supplemental measurements and/or evaluations. If a subject dies during participation in the study or during a recognized follow-up period, the Sponsor should be provided with a copy of any postmortem findings, including histopathology.

For SAEs, new or updated information should be recorded on the originally completed paper SAE Report Form and all changes signed and dated by the investigator or designee. By signing the SAE Report Form, the investigator or designee attests to the accuracy and completeness of the data and that he/she has reviewed and approved the report being submitted. The investigational sites IRB must be notified about SAEs in accordance with the requirements of the governing IRB.

11.6 Prompt Reporting of SAEs to Sponsor

SAEs must be reported promptly to the CRO once the investigator determines that the event meets the protocol definition of a SAE.

Prompt reporting of a SAE requires the following:

• Completion and transmission of the SAE Report Form to the CRO via fax or email within 24 hours of the investigator's knowledge of the event. In parallel, a corresponding AE with the SAE details should be entered into the AE eCRF within 48 hours of submitting the paper SAE Report Form.

Prompt reporting of additional information for previously reported SAEs should follow the same reporting timeframe as initial reports. In addition, the corresponding AE in the AE eCRF (as applicable) should be updated to ensure all data points documented in the AE eCRF are aligned with the matching data points on the paper SAE Report Form.

11.7 Pregnancy Reporting

Pregnancies detected in subjects assigned to study treatment should be reported within 24 hours of investigator's awareness to CRO via fax or email, using the Sponsor's Pregnancy Notification Form. If a female subject becomes pregnant following assignment to study treatment, the study product will be immediately discontinued and the subject will be followed until the outcome of the pregnancy is known.

The CRO should be notified via fax or email of any updates on the status of the pregnancy as soon as the information becomes available by update and/or amendment of the initial pregnancy notification form.

Although pregnancy occurring in a clinical study is not considered to be an AE or SAE, any pregnancy complication or elective termination of a pregnancy, for medical reasons, will be recorded as an AE or SAE and followed as such.

11.8 Transmission of SAE Reports and Pregnancy Notification Forms

Completed SAE Report Forms and completed pregnancy notification forms will be transmitted to the CRO via the fax number provided below:

11.9 Regulatory Reporting Requirements for SAEs

The investigator, or responsible person per local requirements, must comply with the applicable local regulatory requirements related to the reporting of SAEs and IND safety reports to regulatory authorities and their IRB.

12 Statistics

A detailed statistical analysis plan (SAP) will be prepared for this study. The plan will contain a discussion of the statistical methods, a description of the computational algorithms and data handling conventions, and specifications for the data summaries and listings. It will be finalized before database lock.

12.1 Randomization

This is an open-label, non-randomized study.

Clinical Study Protocol Amendment 1 08Oct2018

12.2 Determination of Sample Size

Six subjects per group is the minimum recommendation from FDA guidance "Pharmacokinetics in Patients with Impaired Hepatic Function: Study Design, Data Analysis, and Impact on Dosing and Labeling." A total of 12 subjects with severe liver impairment will be enrolled to meet the combined objectives of effects of liver impairment on the PK of rifaximin.

12.3 Analysis Populations

The Intent-to-Treat (ITT) population will be used for safety analyses. The ITT population will include all subjects who ingested at least one dose of study drug.

The PK population will include subjects from whom sufficient data are obtained for calculation of rifaximin plasma PK parameters.

12.4 Subject Disposition

Subject disposition will be summarized using descriptive statistics.

12.5 Demographic and Baseline Characteristics

Demographic and other baseline characteristics will be summarized using descriptive statistics.

Medical history will be coded using the Medical Dictionary for Regulatory Activities (MedDRA). Medical history data will be listed in subject data listings.

12.6 Analysis Methods

Pharmacokinetic and safety endpoints are shown in Section 5.3 and Section 5.4.

12.6.1 Pharmacokinetic Analyses

All subjects who receive study medication and have sufficient samples collected for valid estimation of PK parameters during any dosing period will be considered evaluable for the PK analyses. Descriptive PK parameters for rifaximin and 25-desacetyl rifaximin will be determined using Phoenix WinNonlin version 6.3 (Pharsight Corporation) or higher.

At a minimum, the following PK Parameters will be calculated, data permitting:

Cmax,ss	Maximum observed concentration at steady-state, observed by inspection of	
	individual study participant plasma concentration time plots.	
Tmax,ss	Time of maximum observed concentration at steady-state, obtained directly	
	from the observed concentration time data	
λz	Terminal phase elimination rate constant, estimated by linear regression of	
	logarithmically transformed concentration versus time data. Calculation of λz	
	requires a minimum of 3 data points after (and not including) Cmax. The	
	adjusted R^2 for the linear regression must be at least 0.80.	
t ¹ / ₂	Terminal phase half-life, estimated using the equation $[\ln(2)/\lambda z]$	
ΑUCτ	At steady state, the area under the plasma concentration time curve from time 0	
	to the end of the dosing interval (12 hours).	
CL/F	Apparent plasma clearance divided by bioavailability, calculated as Dose/AUCt	
(Rifaximin	at steady state.	
only)		

Rifaximin and 25-desacetyl rifaximin plasma concentrations will be summarized by hepatic function group for each collection time point and collection period with statistics of the number of subjects evaluated (N), arithmetic mean, geometric mean, standard deviation, coefficient of variation, median, minimum, and maximum.

An analysis of variance (ANOVA) will be performed and PK parameters of Cmax and AUCτ for rifaximin and 25-desacetyl rifaximin will be natural log transformed prior to analysis. The 90% confidence intervals (CIs) of the hepatic impairment group mean relative to the matched control group mean will be obtained. The effect of hepatic impairment will be assessed by examining the 90% CIs for the mean ratio of the hepatic impairment group relative to the matched healthy group.

A continuous analysis using linear regression will be performed to evaluate the relationship between estimated creatinine clearance and rifaximin CL/F.

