Exploratory: To assess the effect of rifaximin administration on the intestinal microbiome in subjects with severe hepatic impairment (MELD 19 to 25 and MELD >25).

Methodology:

This is a Phase 4, open-label, repeat-dose, parallel-design study in 12 subjects with severe hepatic impairment (MELD 19 to 25 and MELD >25) and 6 healthy subjects with normal hepatic function. At least 6 of the hepatically impaired subjects will have MELD score >25. Efforts will be made to match subjects across groups in terms of age, weight, and sex. Eligible subjects will complete a Screening Period of up to 21 days prior to dosing (Day 1), a 7-day Treatment Period, and Follow-Up by phone 3 (+1) days later. Subjects will be admitted to the Clinical Research Unit (CRU) on the day prior to initiation of dosing (Day -1; CRU admission). A plasma sample for PK analysis will be collected on Day 1 prior to the first dose. Subjects will receive 550 mg rifaximin BID approximately 12 hours apart for 6 days beginning on Day 1 (Baseline). On Day 7 (End of Treatment; EOT), the final dose of study drug will be administered in the morning following an overnight fast of 10 hours. Plasma samples for PK analysis will be collected pre-dose (within 1 hour of the dose) and at 0.25, 0.5, 0.75, 1, 1.5, 2, 4, 6, 8, 10, 12, 16, 20, and 24 hours post-dose. Additionally, a trough blood sample will be collected on Days 2-6, prior to administration of the first daily dose of rifaximin. Subjects will reside in the CRU for 9 days and will be discharged following the final PK sample collection if safety parameters are acceptable to the Investigator. Each subject will be contacted for a follow-up phone call on 3 (+1) Days following end of treatment.

Number of patients planned: N = 18, 12 subjects with liver impairment and 6 matched healthy volunteer subjects. At least 6 of the hepatic impaired subjects will have a MELD score of >25.

Diagnosis and main criteria for inclusion:

Hepatically impaired subjects will be ≥ 18 years of age, have a diagnosis of liver cirrhosis and a MELD score of ≥ 19 at Screening. Note: At least 6 of the hepatically impaired subjects will have a MELD score of ≥ 25 .

Key exclusion criteria:

Subject has known allergy to rifaximin, rifampin, or other rifamycins, excipients and/or vehicles used in the formulation, or any other clinically significant allergies.

Subject has participated in an investigational drug or device study within 30 days prior to Day 1 (Baseline).

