4.1 Disease Background

The magnitude of the health care burden caused by liver disease in the United States (U.S.) is significant from both a societal and health economic perspective. Approximately 2.6 million people have liver disease in the U.S. Cirrhosis is a major cause of much of chronic liver disease (CLD) in the U.S., and is the 12th leading cause of death (Pleis, 2007). Hepatic encephalopathy (HE) is a complication of CLD that strongly impacts survival (Stewart, 2009; Bustamante, 1999), results in frequent hospitalizations, (Leevy, 2007; Poordad, 2007; Bajaj, 2010) increases dependence on care providers (Miyazaki, 2010) and greatly contributes to the clinical and socio-economic burden of CLD. Rifaximin, a minimally absorbed, gutselective antibiotic, has been shown to significantly reduce the risk of overt HE recurrence and HE-related hospitalizations, in a double blind, placebo-controlled, 6-month study enrolling patients with a recent history of recurrent, overt HE, and a Model for End Stage Liver Disease (MELD) score of ≤ 25 (Bass, 2010), with a safety profile similar to placebo. One of the limitations of this study was that only few patients (<9%) with more severe liver disease (MELD \geq 19) were enrolled and adequate pharmacokinetic (PK) and safety data for treatment with rifaximin in this more severe population are not currently available. Therefore, the current study will be conducted to provide rifaximin PK data for patients with MELD scores ≥ 19 .

FDA requires that the sponsor completes post-marketing requirement (PMR) 1615-3 entitled, "A pharmacokinetic trial in patients with severe hepatic impairment (MELD 19 - 25 and MELD > 25). The present trial protocol is designed to meet the PMR objective and is subject to FDA review and approval, under IND 059133.

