4.3 Rationale for the Study

A pharmacokinetic investigation of hepatically impaired subjects (RFHE3002PK) was conducted as a sub-study to Phase 3 open-label study RFHE3002 using a 550 mg BID rifaximin dosing regimen. Systemic exposure to rifaximin was significantly higher in patients with hepatic impairment compared to healthy subjects. Patients with hepatic impairment had mean apparent oral clearance reduced by 88% and the half-life was increased by 2-fold compared to healthy subjects. The mean C_{max} and AUC_{tau} were 6-fold and 11-fold higher, respectively, than in healthy subjects. When the PK parameters were analyzed by

Clinical Study Protocol Amendment 1 08Oct2018

liver function, the mean C_{max} and AUC_{tau} in patients in moderate (Child-Pugh B) hepatic impairment were 28% and 36% higher than in patients with mild (Child-Pugh A) hepatic impairment. The mean C_{max} and AUC_{tau} in patients increased as Model for End Stage Liver Diseases (MELD) score increased as well. Mean steady-state AUC_{tau} values of 118 ng.h/mL, 161 ng.h/mL, and 246 ng.h/mL were observed in Child-Pugh A, Child Pugh B, and Child-Pugh C subjects, respectively.

The clinical trials submitted as part of the approved new drug application (NDA) for rifaximin did not include patients with the most severe hepatic impairment (Model for End-Stage Liver Disease [MELD] score >25) and only limited numbers of patients with Child-Pugh C subjects. Therefore, as part of Phase 4 post marketing requirements requested by FDA, this study is being conducted to characterize the pharmacokinetics of rifaximin in patients with severe hepatic impairment.

5 Study Objectives and Purpose

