5.1 Primary Objective

The primary objective of this study is to characterize the steady state plasma PK of rifaximin (550 mg BID) in subjects with severe hepatic impairment (MELD 19 to 25 and MELD >25), as well as healthy subjects with normal hepatic function.

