7.1 Inclusion/Exclusion for Subjects with Severe Hepatic Impairment

7.1.1 Hepatic Impairment Subject Inclusion Criteria

A subject will be eligible for inclusion in this study if all of the following criteria are met:

- 1. Subject provides written informed consent as documented on the Institutional Review Board (IRB) approved informed consent document.
- 2. Subject is ≥ 18 years of age at Screening.
- 3. Male or non-pregnant, non-breast feeding female.

Clinical Study Protocol Amendment 1 08Oct2018 4. Females of childbearing (reproductive) potential must have a negative serum pregnancy test at Screening and a negative urine pregnancy test at Screening and Day 1, and agree to use an acceptable method of contraception throughout their participation in the study. Examples of acceptable methods of contraception include double barrier methods (condom with spermicide jelly or diaphragm with spermicide), hormonal methods (oral contraceptives, patches or medroxyprogesterone acetate), or an intrauterine device with a documented failure rate of less than 1% per year. Abstinence may be considered an acceptable method of contraception at the discretion of the investigator.

NOTE: Females who have been surgically sterilized (e.g., hysterectomy or bilateral tubal ligation) or who are postmenopausal (total cessation of menses for >1 year) will not be considered "females of childbearing potential."

- 5. Subject has a diagnosis of liver cirrhosis.
- 6. Subject has a MELD score of ≥19 at Screening. Note: At least 6 subjects will have a MELD score of >25.
- 7. Subject is capable of understanding the requirements of the study, is willing to comply with all the study procedures, and is willing to attend all study visits.

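### The planned comparison is one hepatic impairment group against healthy controls, although the primary objective names two MELD strata; no ratio or interval is planned for either stratum

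*Combined protocol and SAP*

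**What the plan says.** Section 5.1 sets the primary objective as characterizing steady-state PK "in subjects with severe hepatic impairment (MELD 19 to 25 and MELD >25), as well as healthy subjects with normal hepatic function". Section 4.1 gives the post-marketing requirement that the trial must meet in the same two strata: "A pharmacokinetic trial in patients with severe hepatic impairment (MELD 19 - 25 and MELD > 25".

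Section 12.2 bases the size on a per-group rule, "Six subjects per group is the minimum recommendation from FDA guidance", and plans 12 impaired subjects; the Synopsis adds 6 healthy subjects.

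The comparative analysis in section 12.6.1, repeated in the Synopsis, is an ANOVA on log-transformed parameters followed by one contrast: "The 90% confidence intervals (CIs) of the hepatic impairment group mean relative to the matched control group mean will be obtained". The Synopsis introduces it as the effect of severe hepatic impairment as a whole. The factor levels are not listed. The rest of the plan does not supply stratum estimates:

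- The only regression relates CL/F to creatinine clearance, not to MELD.
- Section 12.7.1 marks covariate adjustment as not applicable.
- The summary by hepatic function group in 12.6.1 covers plasma concentrations only, and that term is not defined.
- Section 12 defers detail: "A detailed statistical analysis plan (SAP) will be prepared for this study".

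On the strata themselves, only the upper one has an enrolment minimum (section 7.1.1: "Note: At least 6 subjects will have a MELD score of >25"). The inclusion paragraph of the Synopsis words the boundary differently: "At least 6 of the hepatically impaired subjects will have a MELD score of ≥ 25". MELD is assessed at Screening, Day 1 and Day 7 (sections 10.1.1, 10.1.3 and 10.1.6).

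**The concern.** The objective asks for PK in two severity strata, and the analysis as worded returns one number for both. Section 4.3 states that the trials in the approved application included no patients with MELD >25, and that mean Cmax and AUCtau "in patients increased as Model for End Stage Liver Diseases (MELD) score increased as well". If that trend continues above 25, a pooled geometric mean ratio is too low for MELD >25, the stratum with no earlier data, and too high for MELD 19 to 25.

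The pooled ratio would also depend on who happens to enrol. Between 6 and 12 of the 12 impaired subjects may be MELD >25, so the same underlying exposures can give different pooled results. At the extreme, MELD 19 to 25 could have no subjects and its ratio could not be estimated.

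**Working it through.** **Group count.** The plan gives no power calculation, so the only figure to reproduce is the total of 18. Three groups × 6 = 18 matches. Two groups × 6 = 12 does not. The size rationale therefore implies three groups, while the contrast describes two.

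**Bias of a pooled ratio.** Let g be the true geometric mean exposure in MELD >25 divided by that in MELD 19 to 25, and let k of the 12 impaired subjects be MELD >25. On the log scale the pooled mean is the weighted average of the strata, so

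- pooled ratio ÷ MELD 19 to 25 ratio = g^(k/12)
- pooled ratio ÷ MELD >25 ratio = g^(k/12 − 1)

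The documents give no exposure data for MELD >25, so g is assumed. Two values are used: 246/161 = 1.528, the ratio of mean AUCtau in Child-Pugh C to Child-Pugh B (sections 4.2.1 and 4.3), as a stand-in; and 2.

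| g | Split (19 to 25 : >25) | Error for MELD 19 to 25 | Error for MELD >25 |
|---|---|---|---|
| 1 | any | 0 | 0 |
| 1.528 | 6:6 | +23.6% | −19.1% |
| 1.528 | 3:9 | +37.4% | −10.1% |
| 2 | 6:6 | +41.4% | −29.3% |
| 2 | 3:9 | +68.2% | −15.9% |

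**Precision.** The 90% CI is the ratio multiplied and divided by exp(t(0.95, df) × s × √(1/n1 + 1/n2)), with s² = ln(1 + CV²). The documents give no CV, so a range is assumed. At CV 60%, s² = ln(1.36) = 0.3075 and s = 0.5545.

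- Pooled 12 v 6, df 16: exp(1.746 × 0.5545 × 0.5) = 1.62
- Three-level factor, 6 v 6, df 15: exp(1.753 × 0.5545 × 0.577) = 1.75
- Three-level factor, 3 v 6, df 15: exp(1.753 × 0.5545 × 0.707) = 1.99
- Three-level factor, 9 v 6, df 15: exp(1.753 × 0.5545 × 0.527) = 1.67

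| CV | 12 v 6 | 6 v 6 | 3 v 6 | 9 v 6 |
|---|---|---|---|---|
| 40% | 1.40 | 1.48 | 1.61 | 1.43 |
| 60% | 1.62 | 1.75 | 1.99 | 1.67 |
| 80% | 1.85 | 2.04 | 2.39 | 1.92 |

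The pooled figures assume equal strata. If the strata differ, their spread enters the residual of the two-group model: s² + (ln g)² × (n_lo × n_hi/12)/16, where n_lo and n_hi are the numbers in the lower and upper stratum. At 6:6 and CV 60%:

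- g = 1.528: 0.3075 + 0.0337 = 0.3412, multiplier 1.67
- g = 2: 0.3075 + 0.0901 = 0.3976, multiplier 1.73

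When the strata really differ 2-fold, the pooled interval (1.73) is almost as wide as the separate one (1.75).

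**The case against.** The strongest reply is that section 12.6.1 never says the strata are combined. Six per group implies three groups, and the singular wording could be generic language applied to each group. Section 12 defers the methods to a SAP, which is where factor levels and stratum assignment would normally be set. This stands as a limit: pooling is an inference from the wording, not a quoted decision. It does not supply the missing stratum ratios, and the Synopsis, which speaks of severe impairment as a whole, supports the pooled reading. The SAP need only be final before database lock in an open-label study, so stratum contrasts first defined there could be chosen with data in view.

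Second, the objective is to characterize, so descriptive results might be enough. Partly so. But the plan itself chose ratios with 90% CIs to assess the impairment effect, and its by-group summary covers concentrations, not Cmax or AUCtau.

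Third, the size of the error rests on assumptions. That is true: the 1.53 figure is a Child-Pugh ratio of means, not stated to be geometric and not a contrast at MELD 25. Errors of +24% and −19% also lie inside the pooled interval of ×/÷1.62, and are small beside the 11-fold AUCtau difference between impaired and healthy subjects in section 4.3. They are illustrations, and they are errors in what is being estimated, which more subjects at the same split would not remove.

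Fourth, two of the linked points are minor. The Synopsis's alternative boundary is an isolated slip against consistent use of >25 elsewhere, and criterion 6 makes Screening the evident basis for assigning the stratum. It is also fair that, without a minimum for MELD 19 to 25, the fix cannot guarantee a usable estimate in that stratum.

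**Conclusion.** The concern holds and should be fixed. The protocol names two strata in its primary objective, sizes the study in a way that fits three groups, and then specifies no effect estimate for either stratum. Confidence is high that stratum-level ratios are absent from the protocol; that the strata would be pooled is the natural reading only.

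The consequence depends on the unknown difference between strata. There is no bias if they are equal. At 6:6 the pooled ratio is 19% low for MELD >25 and 24% high for MELD 19 to 25 at an assumed 1.53-fold difference, and 29% low and 41% high at an assumed 2-fold difference. With 3 subjects in MELD 19 to 25 and 9 in MELD >25, the error for the lower stratum rises to 37% and 68% respectively.

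**What to change.** In section 12.6.1 and the Synopsis, and then in the SAP:

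- Fit the ANOVA to ln(Cmax), ln(AUCtau) and, as the Synopsis lists it, ln(CL/F), with a three-level factor: healthy, MELD 19 to 25, MELD >25.
- Report each stratum's geometric mean ratio to healthy with its 90% CI as the main results, and keep the combined ratio as supplementary.
- Define hepatic function group as the same three levels and use it for the parameter summaries as well as the concentrations.
- State which MELD assessment assigns the stratum. Screening is the one that inclusion criterion 6 uses; Day 1 MELD could serve as a sensitivity analysis.
- Reconcile the two wordings of the boundary at 25.
- State that the three-group comparison relies on about 6 of the 12 being MELD 19 to 25, report the achieved split, and say in advance how a very small stratum will be presented, for example by individual values and descriptive statistics only.

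The cost is wording, with no change to data collection and no extra subjects, plus attention to the split during enrolment. At CV 60% and 6:6 the 90% CI multiplier widens from 1.62 to 1.75, or from 1.73 to 1.75 if the strata truly differ 2-fold. It is larger for a stratum that enrols few subjects: 1.99 with 3 in MELD 19 to 25.
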